1. METHODS AND DESIGN

1.1. TRIAL DESIGN AND AIMS

The MENDING trial is a phase II proof-of-concept trial of IV guanfacine vs. placebo for the treatment of critical illness delirium. The aims of the trial are the following:

- **Aim 1**: To determine whether IV guanfacine twice a day will increase the number of days alive without delirium and coma (delirium/coma-free days, DCFDs) over 14 days relative to placebo.
- **Aim 2**: To evaluate whether IV guanfacine twice a day will increase days alive and free of mechanical ventilation (ventilator-free days, VFDs) and days alive and free of the ICU (ICU-free days, IFDs) over 28 days relative to placebo.

1.2. RANDOMIZATION AND BLINDING

The trial aims to randomize 50 patients with delirium in the ICU in a 1:1 ratio to IV guanfacine or placebo. A computer-generated randomization scheme (with permuted block sizes) was created by the study's primary biostatistician and uploaded directly into REDCap's randomization module [1-2]. Investigators, patients, and clinicians will be blinded for the duration of the study until the database is locked.

1.3. POWER ANALYSIS AND SAMPLE SIZE

Prior to beginning enrollment, our goal was to enroll and randomize 100 participants. We estimate that the participants in the placebo group will have 6.9±5.2 delirium/coma-free days (DCFDs) during the 14-day interventional study period based on the results from the recently completed Maximizing the Efficacy of Sedation and Reducing Neurological Dysfunction and Mortality in Septic Patients (MENDS2) study that used similar entry criteria [3]. Enrolling 100 patients would provide us at least 80% power to detect a 3 DCFDs

difference between the treatment groups over 14-day period for Aim 1. For Aim 2, we estimate that the participants in the placebo group will have 15.4±10.9 ventilator-free days (VFDs) and 13±10 ICU-free days (IFDs) based on the results from our MENDS2 study. Enrolling 100 patients would provide us at least 80% power to detect a 6 VFDs and 5.6 IFDs difference between the treatment groups over 28-day period.

Due to low enrollment and, given that this is a phase II proof-of-concept trial to guide safety and preliminary efficacy for future work, our final enrollment target was reduced from 100 to 50 with approval from the National Institute of Health and the Data and Safety Monitoring Board.

By analyzing 50 patients, we will have 80% power to detect a difference of 4.2 DCFDs over 14 days between the IV guanfacine and placebo groups. By analyzing 50 patients, we will have 80% power to detect a difference of 8.8 VFDs and 8.1 IFDs over 28 days between the IV guanfacine and placebo groups.

2. OUTCOMES

2.1. PRIMARY OUTCOME

The primary outcome is delirium/coma-free days (number of days alive without delirium or coma) for 14 days starting on the day of randomization.

2.2. SECONDARY OUTCOMES

The secondary outcomes are:

- Ventilator-free days (number of days alive and free of mechanical ventilation) for 28 days starting on the day of randomization.
- Intensive care unit (ICU)-free days (number of days alive and free of ICU) for 28 days starting on the day of randomization.

For VFDs, both invasive and non-invasive ventilation will be taken into account. To account for terminal extubation for comfort care measures, successful ventilator (invasive or non-invasive) discontinuation will be defined as being alive and free of ventilation for 48 hours following discontinuation. For example, if a patient was discontinued from MV and ventilation was initiated again within the next 48 hours or the patient died within the next 48 hours, then the time (<48 hours) that was off ventilation did not count as a ventilator-free day. Similarly, for ICU-free days, successful ICU discharge will be defined as being alive and free of ICU stay for 48 hours following ICU discharge.

2.3. EXPLORATORY OUTCOMES

The exploratory outcomes are:

- 1. Hospital-free days (number of days alive and free of hospital) for 28 days starting on the day of randomization.
- 2. 90-day mortality starting on the day of randomization.

For hospital-free days, successful hospital discharge will be defined as being alive and free of hospital stay for 48 hours following hospital discharge.

2.4. DESCRIPTIVE OUTCOMES

Among others, the following outcomes will be reported as descriptive statistics.

- 1. Co-administration of sedatives, analgesics, and antipsychotics (frequency and quantity of administration) for 14 days starting on the day of randomization.
- 2. Hypotension (refractory systolic blood pressure < 90 mm Hg or mean arterial blood pressure < 65 mm Hg despite ongoing ICU therapies) for 14 days starting on the day of randomization.
- 3. Bradycardia (heart rate < 60 beats per minute despite ongoing ICU therapies) for 14 days starting on the day of randomization.
- 4. Mental status (new, acute neurologic disturbances such as blurred vision, dizziness, weakness, or vertigo) for 14 days starting on the day of randomization.

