3. STATISTICAL ANALYSIS

3.1. STATISTICAL PRINCIPLES

The statistical analyses for all the aims will be conducted as per this SAP and follow the statistical principles described below.

Participant flow diagram of this trial will be reported as specified by the Consolidated Standards of Reporting Trials (CONSORT) 2010 guidelines [4]. The flow diagram will display all stages of the trial such as screening, exclusions, enrollment, randomization, death, and study withdrawal.

Demographic information, clinical characteristics at baseline and study outcomes will be presented for each treatment group. Median and interquartile range (IQR) will be used for describing continuous variables, and frequency (%) will be used for describing categorical variables.

No hypothesis testing for the differences in baseline characteristics between the treatment groups will be conducted as recommended by the CONSORT 2010 guidelines for reporting parallel group randomized clinical trials [4-5].

Statistical significance level will be set at 5% for all outcomes. 95% confidence intervals will be reported with all effect estimates. No multiple comparison adjustments will be made for secondary and exploratory outcomes following the standard practice of analyzing multiple, prospective clinical trial outcomes [6-9]. No subgroup analyses will be conducted.

Missing data will be imputed, and the imputation process will be reported in detail. Since the percentage of missing data is anticipated to be lower than 5%, single imputation is planned to be used.

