3.2. ANALYSIS POPULATION

Analysis population will be based on the modified intent-to-treat (ITT) principle for all outcomes. The analysis cohort will include patients who were randomized and received study drug for all the primary, secondary and exploratory outcomes unless otherwise specified in this SAP.

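### Hypotension and bradycardia in section 2.4 carry no new-onset or post-first-dose condition, so episodes that precede study drug are counted as outcome events

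*Combined protocol and SAP*

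**What the plan says.** Section 2.4 introduces its list with "Among others, the following outcomes will be reported as descriptive statistics". Three of its items matter here:

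- Item 2: "Hypotension (refractory systolic blood pressure < 90 mm Hg or mean arterial blood pressure < 65 mm Hg despite ongoing ICU therapies"), over 14 days from the day of randomization.
- Item 3: "Bradycardia (heart rate < 60 beats per minute despite ongoing ICU therapies) for 14 days starting on the day of randomization".
- Item 4: "Mental status (new, acute neurologic disturbances such as blurred vision, dizziness, weakness, or vertigo) for 14 days", with the same starting day.

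Only item 4 requires the event to be new. Section 3.2 limits the analysis cohort to "patients who were randomized and received study drug", and section 3.1 states that "frequency (%) will be used for describing categorical variables", by treatment group. Section 1.3 explains the reduced sample size partly on the ground that "this is a phase II proof-of-concept trial to guide safety and preliminary efficacy for future work".

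The SAP does not say whether items 2 and 3 are counted per patient, per day or per episode. It gives no interval from randomization to first dose, no baseline heart rate or blood pressure, and no entry limits on either.

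**The concern.** Items 2 and 3 are the only blood pressure and heart rate outcomes that the SAP names, and the trial is meant to inform safety. A reader of the resulting table will want to know how many patients became hypotensive or bradycardic after receiving guanfacine, compared with placebo. As defined, the table answers a different question: how many met the threshold at any time from the start of the randomization day, including before any study drug.

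The cohort rule in section 3.2 does not help. It selects which patients are counted but does not restrict when their events occur. In an ever/never count, a patient who already meets the criterion on the randomization day is scored as an event whatever the drug then does. Such patients add about the same share to both arms and make a real difference look smaller. For a safety table, that error falls on the side of false reassurance.

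**Working it through.** **The plan's own figures.** The SAP states no figure for hypotension or bradycardia. Its primary power figure (section 1.3: 4.2 days, SD 5.2, 50 patients, 80%) reproduces with 25 per arm and two-sided 5% (sidedness is assumed). The standardized difference is 4.2 / (5.2 × √(2/25)) = 2.856, and Φ(2.856 − 1.960) = 81.5%; the noncentral t gives 79.9%. Nothing in that calculation depends on section 2.4, so no stated figure changes.

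**Inputs for the check.** From the SAP: 50 patients allocated 1:1, so about 25 per arm. Assumed, because the documents do not give them:
- p, the share with a new event after first dose among those free of the condition: 10% placebo, 30% guanfacine
- b, the share already affected before first dose: 0 to 40%, the same in both arms in expectation

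**Patients with any event.** Reported share = b + (1 − b)p. The reported difference is then (1 − b)(p_G − p_P). For b = 30%: 0.3 + 0.7 × 0.1 = 37% and 0.3 + 0.7 × 0.3 = 51%, a difference of 14 points = 0.7 × 20.

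| b | Placebo | Guanfacine | Difference (points) | Ratio |
|---|---|---|---|---|
| 0 | 10% | 30% | 20 | 3.00 |
| 10% | 19% | 37% | 18 | 1.95 |
| 20% | 28% | 44% | 16 | 1.57 |
| 30% | 37% | 51% | 14 | 1.38 |
| 40% | 46% | 58% | 12 | 1.26 |

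With an assumed 20% vs 40% the differences are the same, because only (1 − b) matters. The ratio falls from 2.00 to 1.64 at b = 10% and 1.32 at b = 30%.

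**Days with an event.** Let d be the mean number of pre-dose days that count, equal in both arms, and m_P and m_G the mean post-dose days. The difference is (d + m_G) − (d + m_P) = m_G − m_P, which is unchanged. The ratio (d + m_G)/(d + m_P) moves toward 1. A condition that persists after dosing also uses up days on which a new event could have been seen.

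**Chance imbalance.** Equality of b holds only in expectation. With 25 per arm, the SD of the between-arm difference in baseline share is √(2b(1 − b)/25). That is 8.5 points at b = 10%, 11.3 at 20%, 13.0 at 30% and 13.9 at 40%. With no drug effect and p = 10% in both arms, a baseline difference passes into the reported difference multiplied by (1 − p) = 0.9. One SD is then 7.6, 10.2, 11.7 or 12.5 points, which approaches the diluted effect itself at the larger b.

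**Cost of a restricted denominator.** Counting only patients free of the condition leaves 25(1 − b) per arm: 22.5, 20, 17.5 or 15 on average. For 10% vs 30%, power (normal approximation, pooled variance under the null) is 42.1% at b = 0. At b = 30% it is 16.5% for the planned count and 31.0% for the new-onset row. Both are low, but the smaller denominator loses less than the dilution does.

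**The case against.** Several stronger readings are tempting, and the documents do not support them.

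- A reader might infer that the plan presents these as on-treatment safety events. It does not. They are descriptive outcomes in a window from randomization, and section 2.4 names no test or model for them.
- A reader might infer that any drug effect is diluted, or that a patient affected at entry tells us nothing more. That holds for an ever/never count per patient. If days or episodes are counted, such a patient still contributes after dosing and the absolute difference can be intact. The plan does not give the unit, which is the more basic gap.
- A reader might infer a large loss from the ratio falling from 3.0 to about 1.3. The plan reports percentages by arm, and on that scale the same numbers go from 20 points to 12. Low values of b are just as compatible with the documents, including zero, where nothing is lost.
- A reader might infer a bias favouring one arm. Randomization balances pre-dose episodes in expectation, so the issue is attenuation and noise.

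It is also fair to say that the hypotension item must be refractory, and that both items apply only despite ongoing ICU care. These words narrow what counts but do not exclude an episode already present. A common window from randomization is a defensible convention, and the list in section 2.4 is not exhaustive. Section 3.1 promises baseline characteristics by arm, but it does not say that hypotension or bradycardia at first dose will be among them. A separate baseline table would in any case not show which later events were new. Finally, replacing the planned count with a new-onset count alone would lose information on worsening in patients already affected. That objection stands and shapes the remedy.

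**Conclusion.** The point holds in a limited form. As written, items 2 and 3 count pre-existing and pre-dose episodes, while item 4 in the same list does not admit pre-existing ones. For a table of patients with any event, the risk difference is multiplied by (1 − b); for a table of days, only the ratio is diluted, provided pre-dose days are equal. The 18, 16, 14 and 12 points rest on assumed event rates and an assumed b, and the delay from randomization to dosing has not been quantified because the documents do not give it. The consequence is confined to the descriptive tables for hypotension and bradycardia; no power figure and no primary or secondary analysis changes. The case rests on making a safety-relevant table interpretable, since a trial of this size has little power for such contrasts under any definition. The change should be made, because it is cheap and the trial is intended to guide safety.

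**What to change.** In section 2.4, keep the planned count for items 2 and 3 and add to it:

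1. State the counting unit: patients with any event, and days with an event.
2. Add a row, by arm, for patients with onset after the first dose of study drug through day 14, with patients not meeting the criterion at first dose as the denominator.
3. Add a separate row for patients already meeting the criterion at first dose, with their course after dosing, so that worsening is visible.

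The thresholds and the efficacy windows stay as they are. The cost is a few lines of SAP wording, the time of first dose and charted vital signs, and a little more tabulation. The new-onset row has a smaller denominator, which is why it should stand beside the planned count and not replace it.

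### Does the neurologic-symptom item need a written rule for periods when a delirious or comatose patient cannot be asked?

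*Combined protocol and SAP*

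**What the plan says.** Section 2.4 gives four outcomes to be reported descriptively. The fourth is "Mental status (new, acute neurologic disturbances such as blurred vision, dizziness, weakness, or vertigo) for 14 days", counted from randomization. The section names no assessor, schedule or unit of count, and no code for a patient who cannot be assessed.

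Section 1.2 gives the population: "The trial aims to randomize 50 patients with delirium in the ICU".

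Section 3.1 sets the general rules. Categorical variables are summarised simply: "frequency (%) will be used for describing categorical variables". On missing data it says "Missing data will be imputed, and the imputation process will be reported in detail", followed by "Since the percentage of missing data is anticipated to be lower than 5%, single imputation is planned to be used". Neither sentence says which outcomes it covers.

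Section 3.2 states "Analysis population will be based on the modified intent-to-treat (ITT) principle for all outcomes". Its next sentence defines the cohort as randomized patients who received study drug, and there it names the primary, the secondary and the exploratory endpoints but not the descriptive ones.

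Section 1.3 supplies the only relevant figures: a placebo mean of 6.9 delirium/coma-free days (SD 5.2) out of 14, and, for 50 patients, "we will have 80% power to detect a difference of 4.2 DCFDs over 14 days".

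**The concern.** Blurred vision, dizziness and vertigo are mainly known because a patient reports them; weakness can also be found on examination. A delirious or comatose patient often cannot report. Two readings then seem open.

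- **Counted as no event.** The symptom frequency then depends partly on time free of delirium and coma, which is the primary outcome. If guanfacine works, its patients can be asked on more days and may show more symptoms at the same true rate.
- **Counted as missing.** The imputation sentence in section 3.1 has no stated exception, so symptom events might be imputed into a safety table. The under-5% premise also looks doubtful when about half the placebo window is not delirium/coma-free.

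What is at stake is how a safety table reads in a trial that section 1.3 says should inform safety in later work. Few reports from patients who cannot speak for themselves are not evidence of few symptoms.

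**Working it through.** **1. The plan's own figures.** Inputs from section 1.3: placebo mean 6.9, SD 5.2, 50 patients (25 per arm), 80% power. A two-sided 5% test is assumed. Detectable difference = (1.960 + 0.842) × 5.2 × √(2/25) = 4.12 days. At the stated 4.2 days, power is 81.5% (normal) or 79.9% (noncentral t). The delirium/coma-free-day inputs are therefore coherent. The under-5% figure has no stated derivation and cannot be reproduced.

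**2. The 51% against the 5%.** Placebo days not free: 14 − 6.9 = 7.1, and 7.1/14 = 50.7%. Five percent of 14 days is 0.7 day, and 0.7/7.1 = 9.9%. On a patient-day basis the premise would hold only if about 90% of the non-free days fell after death or were still assessable.

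The documents do not give that split. Assume 3 days dead on average: (7.1 − 3)/(14 − 3) = 37.3% of days alive are spent in delirium or coma. If 10% of those cannot be assessed, the share is 3.7%; if 25%, it is 9.3%. The premise may hold or fail.

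The two figures also differ in kind. One is a share of patient-days for a single item. The other is an anticipated percentage with no unit and no outcome attached.

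**3. The possible arm difference.** Assume an equal true daily rate of 5% in both arms, every patient at the mean number of free days, and the full 4.2-day difference (6.9 against 11.1 free days). Let a and b be the detection probabilities on free and non-free days. The share with at least one recorded event is 1 − (1 − 0.05a)^free × (1 − 0.05b)^(14 − free).

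| Detection on free / non-free days | Placebo | Guanfacine | Difference |
|---|---|---|---|
| 100% / 0% | 29.8% | 43.4% | 14 points |
| 100% / 50% | 41.4% | 47.4% | 6.1 points |
| 75% / 50% | 35.8% | 39.2% | 3.4 points |
| 50% / 50% | 29.8% | 29.8% | 0 |

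The lower rows matter because delirium/coma-free days are not restricted to days in the ICU or hospital, and nothing says symptoms are sought after discharge. The 95% half-width for the first row, at 25 per arm, is 1.96 × √[(0.298 × 0.702 + 0.434 × 0.566)/25] = 26.4 points. The 4.2 days is a detectable difference, not an expected effect.

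**4. The effect of the coding choice.** With nothing detected on non-free days, placebo shows 29.8%. With every non-free day imputed at the free-day rate, it shows 1 − 0.95^14 = 51.2%. The second figure gives symptoms to days after death, which the primary outcome counts as not free. Imputing days alive only, with an assumed 2, 3 or 4 days dead, gives 1 − 0.95^12 = 46.0%, 1 − 0.95^11 = 43.1% or 1 − 0.95^10 = 40.1%. The wide gap therefore comes from joining two extremes.

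**5. The texts side by side.** Section 2.4 states a window and does not describe a daily record. If the unit is the patient, someone who could not be asked on some days is not thereby missing. Section 3.1 opens by tying its principles to the aims, and section 1.1 limits the aims to delirium/coma-free, ventilator-free and ICU-free days. Whether the imputation sentence reaches a descriptive symptom item is open; it is not established that it does.

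**The case for a change.** The strongest reply is that this is a systematic ascertainment effect. A wide confidence interval does not cancel it, and a reader of the table could not see it. The first three items in section 2.4 do not depend on asking the patient, and sections 2.2 and 2.3 give 48-hour rules for counting days, so the authors do write such rules where they see a need. Section 3.1 is unqualified on its face, and a clarifying sentence would cost almost nothing.

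Part of this stands. Recording of symptoms may depend on delirium and coma status, and the SAP does not state a policy. But the documents do not allow the size to be estimated: the daily rate, the detection probabilities and the days dead are all assumptions. A coding rule would not remove the dependence either. Assessable days arise after randomization, so they give context and not an adjusted comparison. The most useful context, delirium/coma-free days by arm, is the primary outcome and will be reported anyway. How symptoms are elicited belongs in data-collection material, which this text does not contain. If symptom events were ever imputed, section 3.1 already commits the authors to describe how.

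**Conclusion.** No change follows. This is missing detail on one untested descriptive item, and analysts working from the plan would fill it sensibly by counting patients with an observed event among treated patients in each arm. That reading fits the summary rule in section 3.1 and the analysis population in section 3.2.

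No test, power figure or efficacy conclusion depends on the item. Under the assumed 5% daily rate and the full 4.2-day difference, the artificial arm difference could be anything from 14 points to none, and the ceiling is itself smaller than its 26-point half-width. Neither the 51% against 5% contrast nor the 29.8% against 51.2% contrast is evidence of a fault: the first compares unlike quantities, and the second joins two extremes.

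The conclusion assumes that the item is summarised per patient and that symptoms are not imputed, which is the ordinary practice for a table of this kind. What remains is a caution in interpretation: symptom reports may vary with time free of delirium and coma.

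### Do fixed 14-day percentages for the safety outcomes mislead because the days on which events can be recorded depend on treatment?

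*Combined protocol and SAP*

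**What the plan says.** Section 2.4 lists outcomes that will be described rather than tested. Three concern safety, each over 14 days from randomization: hypotension, "Bradycardia (heart rate < 60 beats per minute despite ongoing ICU therapies) for 14 days starting on the day of randomization", and "Mental status (new, acute neurologic disturbances such as blurred vision, dizziness, weakness, or vertigo) for 14 days starting on the day of randomization". The hypotension definition carries the same reference to ongoing ICU treatment.

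Section 3.1 presents outcomes by treatment group; for categorical variables, "frequency (%) will be used for describing categorical variables". The document gives no event rate per day at risk. It has no rule for days on which a patient is comatose, delirious, discharged or dead, and it does not say where or how often these events are looked for. Section 3.3 says broadly that outcomes will be modeled by regression, but section 2.4 assigns no effect measure to these items.

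Section 1.3 supplies the figures that bear on days at risk: "We estimate that the participants in the placebo group will have 6.9±5.2 delirium/coma-free days (DCFDs) during the 14-day interventional study period", and with 50 patients "we will have 80% power to detect a difference of 4.2 DCFDs over 14 days".

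**The concern.** Blurred vision, dizziness and vertigo generally have to be reported by the patient, which someone in coma or delirium usually cannot do. If guanfacine clears delirium, as Aim 1 hopes, that arm has more days on which symptoms can come to light. Hypotension and bradycardia are defined by reference to ICU treatment. If guanfacine shortens the ICU stay, as Aim 2 hopes, that arm has fewer days on which they can qualify. At the same daily risk in both arms, the raw percentages could then differ, to the drug's disadvantage on symptoms and to its advantage on hemodynamic events. Section 1.3 justifies the smaller sample partly by the trial's role in guiding safety for later work, so a harm masked or invented in this way could be carried forward.

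**Working it through.** **Inputs.** From section 1.3: placebo mean 6.9 delirium/coma-free days (DCFDs), SD 5.2; detectable difference 4.2 days at N = 50. From section 1.2: 1:1 allocation, so 25 per arm. From section 3.1: significance level 5%, taken as two-sided. Assumed, because the document does not give them: daily event rates and ICU days within the 14-day window.

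**The plan's own figure.** A two-sample t-test with SD 5.2 and 25 per arm has 80% power at a difference of 4.205 days. The normal approximation gives 5.2 × √(2/25) × (1.960 + 0.842) = 4.12. The stated 4.2 reproduces.

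**Symptoms, if every DCFD is a day of observation.** The guanfacine mean would be 6.9 + 4.2 = 11.1, a ratio of 11.1/6.9 = 1.61. For the 3-day difference of the 100-patient target it would be 9.9/6.9 = 1.43. With equal daily rate λ, the share with an event is 1 − exp(−λ × days):

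| λ per day | Placebo (6.9 days) | Guanfacine (11.1 days) | Gap, points |
|---|---|---|---|
| 0.01 | 6.7% | 10.5% | 3.8 |
| 0.02 | 12.9% | 19.9% | 7.0 |
| 0.05 | 29.2% | 42.6% | 13.4 |
| 0.10 | 49.8% | 67.0% | 17.2 |

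The standard error of the difference at 25 per arm is √[p₁(1−p₁)/25 + p₂(1−p₂)/25]. This is about 10 points at λ = 0.02 and 13 points at λ = 0.05. In patients, the gaps are 3.2 against 5.0 and 7.3 against 10.6.

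**Symptoms, if recorded only in the ICU.** Assume ICU days within the window of 12 (placebo) and 7 (guanfacine), with all days that are not delirium/coma-free spent alive in the ICU. Those days number 14 − 6.9 = 7.1 and 14 − 11.1 = 2.9. Reportable days are then 12 − 7.1 = 4.9 and 7 − 2.9 = 4.1, and at λ = 0.02 the percentages are 9.3% and 7.9%. The direction has reversed. With 12 against 10 ICU days, reportable days are 4.9 and 7.1 and the percentages are 9.3% and 13.2%, so it turns back. The sign depends on recording practice and length of stay.

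**Hypotension and bradycardia, if recorded only in the ICU.** At λ = 0.05, 12 against 7 ICU days gives 45.1% against 29.5%; 12 against 10 gives 45.1% against 39.3%. With 12 against 7 days and a true rate ratio of 1.5, guanfacine would show 1 − exp(−0.05 × 1.5 × 7) = 40.8% against 45.1%. These ICU days are assumptions. The plan's 13 placebo ICU-free days are over 28 days, and 28 − 13 = 15 also counts days after death.

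**The alternative, events per day at risk.** Suppose half of patients have a daily risk of 1% and half 9%, the same in both arms. On placebo all spend 12 days in the ICU; on guanfacine the low-risk patients spend 4 and the high-risk patients 10. Per pair of patients:
- placebo: (0.01 × 12 + 0.09 × 12)/24 = 1.20/24 = 0.050
- guanfacine: (0.01 × 4 + 0.09 × 10)/14 = 0.94/14 = 0.067

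The rate ratio is 1.34 although no patient's daily risk has changed. It arises because the lower-risk patients leave the ICU sooner.

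**The case for a change.** The strongest case for a change is the hemodynamic one, because there the raw percentage can hide harm: in the example above, a 50% higher daily rate appears as a slightly lower percentage. With 25 per arm no formal safety conclusion will be drawn, so readers will rely on these side-by-side percentages. Daily delirium, coma and ICU status must be collected anyway for the primary and secondary outcomes, so denominators would cost little.

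Two parts of this stand. Days of observation may differ by arm if the drug works, and the plan does not say how non-assessable, discharged and dead days are treated. The rest is weaker. The reference to ongoing ICU treatment can be read as a severity criterion rather than a limit on where events are recorded. Weakness can be seen by a clinician without self-report, and the list of symptoms is open-ended. The document does not say that each event is reduced to ever/never per patient; a count of affected days would also fit. DCFDs are only a proxy for assessable days. The 4.2 days is a detectable difference, not a forecast.

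**Conclusion.** No change to the plan follows. The share of patients with an event in a fixed window from randomization compares the groups as randomized and describes the total effect of assignment, including any effect through earlier waking or earlier discharge. A rate per delirium/coma-free or ICU day answers a different question and uses a denominator affected by treatment, so it trades one distortion for another. Statisticians could reasonably differ on whether to show it, and a rate ratio with a confidence interval would add inference to outcomes that section 2.4 keeps descriptive.

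The possible distortion in symptoms is 3.8 to 17.2 points for daily rates of 0.01 to 0.10, if every delirium/coma-free day is observed and the drug delivers the full 4.2 days. It is about one standard error or less at rates up to 0.05, and it can reverse if recording stops at ICU discharge. For ICU-tied events the size rests wholly on assumed ICU days.

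What remains is missing detail that analysts can fill when reporting: days alive and assessable, and ICU days alive, by arm beside the percentages, with a note on how the other days were handled. Any rate per such day should be labelled descriptive and not a randomized comparison. None of this corrects a wrong result or conclusion.
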